10.2 Clinical Laboratory Parameters

Descriptive statistics (n, mean, SD, minimum, median, and maximum) for clinical laboratory values (in SI and conventional units) and change from baseline values will be presented by treatment group at each assessment timepoint (including the end of the DBTP) for the following clinical laboratory parameters:

Hematology:	Hematocrit, hemoglobin, HbA1c, red blood cell count, mean corpuscular volume, mean corpuscular hemoglobin, mean corpuscular hemoglobin concentration, reticulocytes, white blood cell count, absolute neutrophils, absolute lymphocytes, absolute monocytes, absolute eosinophils, absolute basophils, neutrophils/leukocytes (%), lymphocytes/leukocytes (%), monocytes/leukocytes (%), eosinophils/leukocytes (%), basophils/leukocytes (%), and platelets,
Chemistry:	Albumin, alkaline phosphatase (ALP), aspartate transaminase (AST), alanine aminotransferase (ALT), total bilirubin, direct bilirubin, blood urea nitrogen, gamma-glutamyl transferase, calcium, creatinine, glucose, insulin, cholesterol, triglycerides, phosphate, potassium, Prolactin, lactate dehydrogenase, sodium, chloride, total protein, uric acid, creatine phosphokinase, and Thyroid-stimulating hormone (TSH) (reflex T3 and T4),

Urinalysis: Specific gravity, pH, protein, glucose, ketones, nitrates, blood, red blood cells, white blood cells, casts, epithelial cells, crystals, and granulation.

Clinical laboratory values will be considered to be potentially clinically significant (PCS) if they meet either the low or high PCS criteria listed in Table 10-2. The number and percentage of patients who have PCS post-baseline clinical laboratory values will be tabulated by treatment group for the DBTP. The percentages will be calculated relative to the number of patients with available non-PCS baseline values and at least one post-baseline assessment. The numerator is the total number of patients with available non-PCS baseline values and at least one PCS post-baseline value.

A supportive listing of patients with PCS post-baseline values will be provided including the patient ID, baseline, and post-baseline values (including non-PCS values). A listing of all AEs for patients with PCS clinical laboratory values will also be provided.

Shift tables from baseline to end of the DBTP for clinical laboratory parameters will be presented by treatment group for the following categories: low, normal, and high, which are provided by the laboratory vendor.

Criteria for potential Hy's Law cases is defined by a postbaseline elevation of alanine aminotransferase (ALT) or aspartate aminotransferase (AST) \ge 3 × ULN, along with total bilirubin (TBL) \ge 2 × ULN and a non-elevated alkaline phosphatase (ALP) < 2 × ULN, all based on blood draws collected within a 24-hour period. Patients who meet the potential Hy's Law criteria during the DBTP will be summarized. Support listings will also be provided.

Laboratory Parameter	SI Unit	Conversion Factor ^a	Conventional Unit	PCS Criteria ^b Low Values	PCS Criteria ^b High Values
Hematology					
Hemoglobin	g/L	0.1	g/dL	\leq 0.9 × LLN	
Hematocrit	%	1	%	$\leq 0.9 \times LLN$	
Abs Neutrophils (ANC)	10 ⁹ /L	1	10 ⁹ /L	< 1.0	
Platelet count	10 ⁹ /L	1	10 ⁹ /L	≤ 75	≥ 700
White cell count	10 ⁹ /L	1	10 ⁹ /L	≤ 2.5	≥ 15
Chemistry					·
Albumin	g/L	0.1	g/dL	< 2.5	
Alkaline phosphatase	U/L	1	U/L		$\geq 2 \times ULN$
ALT	U/L	1	U/L	_	\geq 3 × ULN
AST	U/L	1	U/L		\geq 3 × ULN
Blood urea nitrogen (BUN)	mmol/L	2.8003	mg/dL		≥ 30
Calcium	mmol/L	4.008	mg/dL	< 7	> 12
Chloride	mmol/L	1	mg/dL	< 90	> 115
Total Cholesterol (fasting)	mmol/L	38.6698	mg/dL	_	≥ 300
СРК	U/L	1	U/L		\geq 5 × ULN
Creatinine	mcmol/L	0.0113	mg/dL	_	> 1.3 × ULN
Glucose (fasting)	mmol/L	18	mg/dL	< 45	> 160
LDL Cholesterol (fasting)	mmol/L	38.6698	mg/dL	_	> 200
Potassium	mmol/L	1	mEq/L	< 3	> 5.5
Prolactin	mIU/L	21.2766	ng/ml		> 200
Sodium	mmol/L	1	mEq/L	< 130	> 150
Total bilirubin	mcmol/L	0.0585	mg/dL	_	$\geq 2 \times ULN$
Triglycerides (fasting)	mmol/L	88.6	mg/dL		≥ 300
Urinalysis					
Protein					At least 2 +
Glucose					At least 2 +
Blood					At least 2 +

Table 10-2: Criteria for Potentially Clinically Significant Clinical Laboratory Tests

a Conversion factor from SI units to traditional units.

b Criteria refer to conventional units.

ALT = alanine aminotransferase; AST = aspartate aminotransferase; CPK=creatine phosphokinase; LLN = lower limit of normal of laboratory reference range; PCS = potentially clinically significant; SI = *Le Système International d'Unités* (International System of Units); ULN = upper limit of normal of laboratory reference range.

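### SAP Table 10-2 prints the prolactin conversion factor the wrong way round: applied to mIU/L data, it puts the > 200 ng/mL flag at 9.4 mIU/L instead of about 4,000 to 7,200 mIU/L

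*SAP*

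**What the plan says.** SAP Section 10.2 flags a laboratory value as potentially clinically significant (PCS) when it meets a limit in Table 10-2. The prolactin row reads "Prolactin mIU/L 21.2766 ng/ml", with a high limit of > 200 and no low limit. Two footnotes govern every row. Footnote a describes the factor: "Conversion factor from SI units to traditional units". Footnote b fixes the scale of the limits: "Criteria refer to conventional units". The prolactin limit is therefore > 200 ng/mL.

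The same section plans descriptive statistics "for clinical laboratory values (in SI and conventional units) and change from baseline values will be presented by treatment group", and prolactin is in the list of chemistry parameters. For PCS percentages it sets the denominator, "The percentages will be calculated relative to the number of patients with available non-PCS baseline values and at least one post-baseline assessment", and the numerator, "The numerator is the total number of patients with available non-PCS baseline values and at least one PCS post-baseline value".

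A second row in the table has a unit problem: "Chloride mmol/L 1 mg/dL". The comparable electrolyte row is "Sodium mmol/L 1 mEq/L".

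**The concern.** The footnotes leave one reading: conventional value = SI value × factor. For prolactin that means each mIU/L counts as more than 21 ng/mL. On the usual unit relation, one ng/mL corresponds to some tens of mIU/L, so the factor from mIU/L to ng/mL must be below 1. The printed number looks like the reciprocal of the one intended.

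What is at stake is the safety reporting of prolactin. The PCS percentage leaves out anyone already flagged at baseline. An inverted factor would therefore not merely inflate the count: patients wrongly flagged at baseline drop out of both numerator and denominator, and a true on-treatment rise in one of them would not be counted. Prolactin has some importance here because Protocol Section 2.1 links the drug's low striatal D2 occupancy to a low hyperprolactinemia liability.

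**Working it through.** **Inputs from SAP Table 10-2:** factor f = 21.2766 (mIU/L to ng/mL), limit L = 200 ng/mL, and the direction set by footnote a.

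**Input assumed:** k = mIU/L per ng/mL. The documents do not give it, so a range of 20 to 36 is used, together with the table's own constant read as k = 21.2766.

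**1. Where the printed figure comes from.** 1/0.047 = 21.2766. The printed number is the exact reciprocal, to four decimals, of 0.047, which lies between 1/36 = 0.028 and 1/20 = 0.050. It does not reproduce as an SI-to-conventional factor for any k in the range.

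**2. Do the other rows follow footnote a?** Hemoglobin and albumin (g/L × 0.1 = g/dL) do so by decimal arithmetic alone. The rows that convert moles to mass were checked as molar mass × unit scale:

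| Row | Computed SI-to-conventional factor | Printed |
|---|---|---|
| BUN | 2.801 | 2.8003 |
| Calcium | 4.008 | 4.008 |
| Cholesterol | 38.665 | 38.6698 |
| Creatinine | 0.01131 | 0.0113 |
| Glucose | 18.016 | 18 |
| Total bilirubin | 0.05847 | 0.0585 |
| Triglycerides | 88.57 | 88.6 |

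All agree within about 0.1%. Some factors are above 1 and some below, so the direction has been respected row by row. Prolactin is the exception.

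**3. The flag as printed.** L/f = 200/21.2766 = 9.40 mIU/L. This uses only the table and its footnotes.

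**4. The flag with the factor turned round, and the size of the error.** Correct factor = 1/k; correct flag = 200k; error ratio = f × k; printed flag in true ng/mL = 9.40/k.

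| k (mIU/L per ng/mL) | Correct factor | Correct flag (mIU/L) | Error ratio | Printed flag in true ng/mL |
|---|---|---|---|---|
| 20 | 0.050 | 4,000 | 425.5 | 0.47 |
| 21.2766 | 0.047 | 4,255 | 452.7 | 0.44 |
| 36 | 0.028 | 7,200 | 766.0 | 0.26 |

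As an illustration, 300 mIU/L becomes 300 × 21.2766 = 6,383 ng/mL as printed, and 300/21.2766 = 14.1 ng/mL with the reciprocal.

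**5. Consequence by source unit**, which the documents do not state:
- *Data in mIU/L, converted with this factor:* ng/mL summaries are 426 to 766 times too high, and the PCS row flags anything above 9.4 mIU/L. If most patients exceed that at baseline, the eligible denominator nearly empties. That is an assumption, since the documents give no prolactin distribution.
- *Data in ng/mL:* the PCS row is right. SI values derived by dividing by the factor are too low by the same ratio: 200 ng/mL would appear as 9.4 mIU/L instead of 4,000 to 7,200.
- *Both units supplied by the laboratory:* no output changes.

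The shift tables use categories from the laboratory vendor and are unaffected in every case.

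**6. Chloride.** A factor of 1 from mmol/L fits mEq/L for a monovalent ion, as the sodium and potassium rows show. It does not fit mg/dL. The limits of < 90 and > 115 can stay; only the unit label is wrong.

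**The case against.** The strongest objection is that the documents do not show which cell is wrong. The relation between mIU/L and ng/mL is brought in from outside, and swapped unit labels would also reconcile the row: with ng/mL as the first unit and mIU/L as the second, 21.2766 would be right and the limit would be 200 mIU/L. That reading goes against the printed SI and conventional column headings. It would also put the limit at 200/36 = 5.6 to 200/20 = 10 ng/mL over the same assumed range, so the inverted factor is the better explanation. What stands is that the relation is an assumption, that the upper end of 7,200 rests wholly on k = 36, and that the laboratory should confirm the row before it is changed.

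The second objection is that no wrong output is certain. Samples go to a central laboratory, table specifications sit in a separate document (SAP Section 2), and Protocol Section 9 requires blinded data reviews before unblinding. A discrepancy of about 450-fold would probably be noticed. This is fair, and it is why the effect is stated as conditional. None of it corrects the rule in the SAP, however, and with ng/mL data the PCS row would look normal and give no warning.

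Third, laboratory analyses are descriptive, prolactin is one row among many, and chloride is only a label. All of that stands; chloride alone would be clerical.

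**Conclusion.** The prolactin row is wrong as written. Followed literally, it places a 200 ng/mL safety flag at 9.4 mIU/L, a true concentration of 0.26 to 0.47 ng/mL. The placement at 9.4 mIU/L follows from the SAP alone. The corrected flag and the 426- to 766-fold error rest on the assumed 20 to 36 mIU/L per ng/mL, but the direction of the error is the same across that range. Whether any table is affected depends on the unit the laboratory supplies and on whether programs use the factor. The reach is limited to descriptive prolactin summaries and the prolactin PCS row. It should be corrected because the SAP is the specification for a safety threshold and the correction is cheap.

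**What to change.** - Ask the central laboratory which unit it reports for prolactin and which assay factor it uses. Have the whole row confirmed at the same time, including the unit of the limit.
- In SAP Table 10-2, replace 21.2766 with its reciprocal (about 0.047), or with the laboratory's own SI-to-conventional factor.
- Check any program that reads the table's factors, for both the ng/mL and the mIU/L outputs.
- Change the chloride conventional unit from mg/dL to mEq/L.
- Leave the 200 ng/mL limit and the chloride limits unchanged.

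The cost is two table cells, one laboratory query and a programming check.

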10.3 Vital Signs

Descriptive statistics (n, mean, SD, minimum, median, and maximum) for vital signs assessments (systolic and diastolic blood pressures, pulse rate, weight, temperature, BMI and waist) and changes from baseline values at each assessment visit and at the end of DBTP will be presented by treatment group. For systolic and diastolic blood pressure and pulse rate, measurements will be measured after at least 5 minutes in the supine position and after at least 2 minutes in the standing position. Descriptive statistics for systolic and diastolic blood pressure and pulse rate in the supine position and in the standing position will be presented separately.

Vital sign values will be considered to be PCS if they meet both the observed value criteria and the change from baseline value criteria that are detailed in Table 10-3. The number and percentage of patients who have PCS post-baseline vital sign values will be tabulated by treatment group for the DBTP. The percentages will be calculated relative to the number of patients who have available baseline values and at least 1 post-baseline assessment. The numerator will be the total number of patients with available baseline values and at least 1 PCS post-baseline value.

A listing of all patients with PCS post-baseline values will be provided and will include the patient ID, baseline, all post-baseline (including non-PCS) value and change from baseline. In addition, a listing of all AEs for patients who had PCS vital sign values will be provided.

The number and percentage of patients with orthostatic hypotension will be provided by treatment group. Orthostatic hypotension is defined as a reduction of ≥ 20 mm Hg in systolic BP or a reduction of ≥ 10 mm Hg in diastolic BP measured when the patient changes from the supine position to the standing position. Standing measurements should be taken after sufficient amount of time has been given to allow the blood pressure to equilibrate in the standing state.

A supportive listing of patients with orthostatic hypotension will be provided including the Patient ID, baseline and post-baseline systolic and diastolic BP values (supine and standing).

Vital Sign, unit	Flag	Criterion Value ^a	Change From Baseline ^a
Sustalia bland program mm Ha	High	≥ 180	Increase of ≥ 20
Systolic blood pressure, mm Hg	Low	≤ 90	Decrease of ≥ 20
	High	≥ 105	Increase of ≥ 15
Diastolic blood pressure, mm Hg	Low	≤ 50	Decrease of ≥ 15
D las motor have	High	≥ 120	Increase of ≥ 15
Pulse rate, bpm	Low	≤ 50	Decrease of ≥ 15
xx7 * 1 / 1 h	High	—	Increase of $\geq 7\%$
Weight, kg ^b	Low		Decrease of $\geq 7\%$

Table 10-3: Criteria for	Potentially Clinica	lly Significant Vi	tal Signs
	i otentiany ennica	ny Significant vi	un signs

a A post-baseline value will be considered potentially clinically significant if it meets both criterion value and change from baseline value.

b Weight change is relative to baseline.

bpm = beats per minute.

10.4 Electrocardiograms

Descriptive statistics (n, mean, SD, minimum, median, and maximum) for 12-lead ECG assessments (eg, heart rate, QRS duration, PR interval, RR interval, uncorrected QT interval, and corrected QT [QTc] intervals) and changes from baseline values at each assessment visit and at the end of DBTP will be presented by treatment group. QTc interval will be calculated using both Bazett (QTcB = QT/(RR)^{1/2}) and Fridericia (QTcF = QT/(RR)^{1/3}) corrections; if RR is not available, it will be replaced with 60/heart rate in the correction formula.

ECG parameter values will be considered PCS if they meet or exceed the criterion value or the change from baseline value listed in Table 10-4. The number and percentage of patients who have PCS post-baseline ECG values will be tabulated by treatment group for the DBTP. The percentages will be calculated relative to the number of patients with available non-PCS baseline values and at least 1 post-baseline assessment for PCS criteria based on the actual values and the percentages will be calculated relative to the number of patients who have available baseline values and at least 1 post-baseline assessment for PCS criteria based on changes. The numerator will be the total number of patients with available non-PCS baseline value.

A listing of all patients with PCS post-baseline values will be provided and will include the patient ID, baseline, all post-baseline (including non-PCS) values, and change from baseline. In addition, a listing showing all AEs that occurred in patients who had post-baseline PCS ECG values will be provided.

A shift table from baseline to the end of study in the overall interpretation of the ECG will be presented by treatment group for the following categories: normal; abnormal, not clinically significant; abnormal, clinically significant. A listing showing patients with post-baseline clinically significant ECG abnormalities according to the overall interpretation will be provided.

Parameter	Unit	Criterion Value ^a	Change from Baseline ^a
QRS duration	msec	≥ 150	—
PR interval	msec	≥ 250	_
QTcB	msec	\geq 480	_
QTcB	msec	≥ 500	
QTcF	msec	\geq 480	_
QTcF	msec	≥ 500	
QTcB	msec		Increase of >30 and ≤ 60
QTcB	msec		Increase of > 60
QTcF	msec		Increase of >30 and ≤60
QTcF	msec		Increase of > 60

Table 10-4: Criteria for Potentially Clinically Significant Electrocardiographic Values

a A post-baseline value will be considered potentially clinically significant if it meets the criterion value or the change from baseline value.

 $PCS = potentially clinically significant; QTcB = QT interval/(RR)\frac{1}{2}; QTcF = QT interval/(RR)\frac{1}{3}.$

10.5 Other Safety Parameters

Other safety parameters include the C-SSRS, YMRS, AIMS, BARS and SAS.

10.5.1 Columbia-Suicide Severity Rating Scale (C-SSRS)

The number and percentage of patients with suicidal ideation and suicidal behavior as recorded on the C-SSRS will be summarized by treatment group for lifetime history (assessed at the screening visit), during the DBTP and during the post DBTP. The distribution of responses for most severe suicidal ideation and most severe suicidal behavior will be also presented by treatment group for lifetime history, during the DBTP and during the post DBTP. The baseline of suicidal ideation and suicidal behavior is defined as the last non-missing "since last visit" assessment before the first dose of double-blind study drug. The severity of suicidal ideation will be presented in a decreasing order as below:

- Active suicidal ideation with specific plan and intent
- Active suicidal ideation with some intent to act, without specific plan
- Active suicidal ideation with any methods (not plan) without intent to act
- Non-specific active suicidal thoughts
- Wish to be dead

The severity of suicidal behavior will also be presented in a decreasing order as below:

- Completed Suicide
- Actual attempt

- Interrupted attempt
- Aborted attempt
- Preparatory acts or behavior

For the distribution of responses, each patient will be counted only once under the most severe category across all visits during the specific period for suicidal ideation and separately for suicidal behavior.

Supportive listing for patients with suicidal ideation or with suicidal behavior during the study will be provided and will include the Patient ID, treatment group, visit number, lifetime history, and post-baseline values for each patient. A listing of all AEs for patients with suicidal ideation or suicidal behavior will also be provided.

In addition, the number and percentage of patients with the following emergence of suicidal ideation or of suicidal behavior during the DBTP will be summarized by treatment group:

- Emergence of suicidal ideation (no suicidal ideation at Baseline, and any type of suicidal ideation post-Baseline)
- Emergence of serious suicidal ideation (no suicidal ideation at Baseline, and any serious suicidal ideation [Active suicidal ideation with specific plan and intent, or Active suicidal ideation with some intent to act, without specific plan] post-Baseline)
- Worsening of suicidal ideation (most severe suicidal ideation post-Baseline was more severe than it was at Baseline)
- Emergence of suicidal behavior (no suicidal behavior at Baseline, and any type of suicidal behavior post-Baseline)

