5.2 Patient Exclusion Criteria

Patients meeting any of the following criteria will be excluded from the study:

- The patient experiences a ≥ 25% decrease in the rater-administered MADRS total score between Screening (Visit 1) and Baseline (Visit 2);
- 2. In the opinion of the Investigator, the patient has a significant risk for suicidal behavior during the course of his/her participation in the study or
 - a. At Screening (Visit 1), the patient scores "yes" on Items 4 or 5 in the Suicidal Ideation section of the C-SSRS with reference to a 6-month period prior to screening; or
 - b. At Screening (Visit 1), the patient has had 1 or more suicidal attempts with reference to a 2-year period prior to screening; or
 - c. At Baseline (Visit 2), the patient scores "yes" on Items 4 or 5 in the Suicidal Ideation section of the C-SSRS with reference to Screening; or
 - d. At Screening (Visit 1) or Baseline (Visit 2), scores ≥ 4 on Item 10 (suicidal thoughts) on the rater-administered MADRS; or
 - e. Considered to be an imminent danger to himself/herself or others;
- The patient is pregnant or breast-feeding. Female patients of childbearing potential must have negative urine and serum pregnancy tests at Screening (Visit 1). On Day 1 (Baseline/Visit 2), female patients of childbearing potential must have a negative urine pregnancy test prior to study drug administration;
- 4. Within 12 months of screening, the patient has a confirmed DSM-5 psychiatric diagnosis other than Bipolar Disorder or MDD, including:
 - a. Schizophrenia or other psychotic disorder;
 - b. Anxiety disorders such as panic disorder, obsessive-compulsive disorder, general anxiety disorder, or post-traumatic stress disorder as a primary diagnosis (however, anxiety symptoms may be allowed, if secondary to Bipolar Disorder or MDD, provided these symptoms do not require current treatment);
 - c. Eating disorder;
 - d. Personality disorder;
 - e. Moderate or severe substance use disorder (including for cannabis, excluding for nicotine);
 - f. Any other psychiatric condition (other than Bipolar Disorder or MDD) that has been the main focus of treatment within 12 months of screening;

ITI-007-403 Protocol

- 5. Patients who have experienced hallucinations, delusions, or any other psychotic symptomatology in the current depressive episode may be allowed as long as these symptoms are not attributable to a primary DSM-5 diagnosis other than Bipolar Disorder or MDD, as described in Exclusion Criterion #4;

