9.4 Statistical Analysis Methodology

Categorical variables (eg, AEs) will be summarized using the number and percentage of patients in specified categories. Unless otherwise stated, the calculation of percentages will be based on the number of patients in the analysis set of interest. Continuous variables (eg, MADRS total score) will be summarized using descriptive statistics including number of patients, mean, standard deviation, median, minimum, and maximum.

For analysis purposes, baseline is defined as the last non-missing measurement before the first dose of study drug. Assessments on Day 1 for which times are recorded will be

considered baseline if the assessment time is before the time of the first dose of study drug.

Unless stated otherwise, statistical tests will be performed at a 2-sided significance level of 0.05, leading to 95% (2-sided) confidence intervals (CIs).

For efficacy analyses in which study site is a factor, a small site will be defined as a site with less than 2 patients in at least one treatment group for each specific analysis set (ie, the mITT Set, the Bipolar Disorder with mixed features based on mITT Set, the MDD with mixed feature based on mITT Set, and the bITT Set). Small sites in each specific analysis set will be pooled to form pseudo-sites so that each treatment group includes at least 2 patients within the site. Pooling will be performed separately for each analysis set but using the same algorithm described as the following:

Based on the number of patients, small sites will be ordered from the largest to the smallest, and sites of the same size will be ordered from the largest site code to the smallest site code. The pooling process starts with the largest small site from the top, which will be pooled with the smallest from the bottom until a non-small site is formed. The process will be repeated using the small sites left out after the first pass. If any sites are left out at the end of the process, they will be pooled with the smallest pseudo site. If there is more than 1 smallest pseudo site, the pseudo site with the smallest site code will be selected. In case the pseudo site formed by pooling all small sites is still a small site, it will be pooled with the smallest non-small site. If there is more than 1 smallest non-small site. If there is more than 1 smallest non-small site. If there is more than 1 smallest non-small site.

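### Does the SAP's row for emergent serious suicidal ideation lose patients who enter with milder ideation?

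*SAP*

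**What the plan says.** SAP 10.5.1 lists four rows for change from Baseline during the double-blind treatment period (DBTP), each by treatment group. Three concern ideation:

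- a row for new ideation of whatever level, open to patients who had none at Baseline
- "Emergence of serious suicidal ideation (no suicidal ideation at Baseline, and any serious suicidal ideation" post-Baseline, where serious means the two most severe of the five C-SSRS ideation levels (4 and 5)
- "Worsening of suicidal ideation (most severe suicidal ideation post-Baseline was more severe than it was at Baseline"

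The fourth is emergence of suicidal behavior, which again starts from none at Baseline.

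The same section also plans a period-by-period display: "The distribution of responses for most severe suicidal ideation and most severe suicidal behavior will be also presented by treatment group". One of its periods is the DBTP. Levels 4 and 5 are separate categories, and each patient is counted once, under the worst level reached. A supportive listing is planned as well.

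On entry, exclusion 2a in Protocol 5.2 bars a yes "on Items 4 or 5 in the Suicidal Ideation section of the C-SSRS with reference to a 6-month period prior to screening", and exclusion 2c bars a yes at Visit 2 "on Items 4 or 5 in the Suicidal Ideation section of the C-SSRS with reference to Screening". Levels 1 to 3 are not excluded by item score.

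**The concern.** By its label, the serious-ideation row should show everyone who newly develops intent or a plan. By its definition, it shows only those who had no ideation at all at Baseline. A patient who enters with a wish to be dead (level 1) and progresses to a specific plan with intent (level 5) is not in it. That patient is in the worsening row, but so is one who moves only from level 1 to level 2.

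The row also states no denominator. The default in Protocol 9.4 is "Unless otherwise stated, the calculation of percentages will be based on the number of patients in the analysis set of interest". Under it, patients at levels 1 to 3 would sit in the denominator but could never enter the numerator. The laboratory rule in SAP 10.2 works differently: "The numerator is the total number of patients with available non-PCS baseline values and at least one PCS post-baseline value". By analogy, one might expect a baseline condition of no serious ideation here.

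Suicidality measured by the C-SSRS is a named safety objective. If serious ideation arising on treatment were really missing from the tables, that would be a reporting gap worth closing.

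**Working it through.** No sample size, power or alpha is involved. The check is to enumerate the possible moves and see which planned display contains each.

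**Inputs**

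- Ideation levels 1 to 5 (Protocol 8.3.6.2), with 0 for none. Serious is 4 or 5 (SAP 10.5.1).
- Baseline is the last since-last-visit assessment before the first dose (SAP 10.5.1). Protocol 8.3.6.2 uses that version at every visit after Screening, so Baseline is normally the Visit 2 form. Exclusion 2c acts on the same form.
- Eligible Baseline levels are therefore 0, 1, 2 and 3.

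**Counts of (Baseline level, worst DBTP level) pairs**

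- All pairs: 4 × 6 = 24.
- Moves from non-serious to serious: 4 × 2 = 8.
- Of these, from level 0: 1 × 2 = 2. From levels 1 to 3: 3 × 2 = 6.
- All rises: 5 + 4 + 3 + 2 = 14, of which 8 end at level 4 or 5 and 14 − 8 = 6 end lower.

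| Planned display | Pairs covered | Of the 8 moves to serious | Of the 6 starting at level 1–3 |
|---|---|---|---|
| Emergence of ideation | 5 | 2 | 0 |
| Emergence of serious ideation | 2 | 2 | 0 |
| Worsening | 14 | 8 | 6 |
| DBTP distribution, levels 4 and 5 | 8 | 8 | 6 |

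The first three lines confirm the literal reading. The serious row omits 6 of 8 moves, and the worsening row mixes those 6 with 8 others. Taking emergence of ideation away from worsening leaves 14 − 5 = 9 pairs: the 6, plus (1,2), (1,3) and (2,3). So the change-from-baseline rows alone do not isolate the 6.

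The last line settles the matter. Levels 4 and 5 of the DBTP distribution contain exactly the 8 moves and nothing else. Subtracting the serious row leaves 8 − 2 = 6, which are exactly the moves said to be missing. A row redefined as level 0 to 3 at Baseline and level 4 or 5 afterwards would also hold these 8 pairs. It would print the sum of two categories that are already planned, by arm.

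**The rule across rows.** All three emergence rows start from none at Baseline, and a rise in ideation from an existing level goes to worsening. The scheme is consistent, and each condition is stated with its row. Protocol 9.4.6 asks only for the number and percentage with ideation or behavior, plus listings. SAP 10.5.1 already gives more than that.

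**The laboratory comparison.** The SAP has no single convention. For vital signs (SAP 10.3) the denominator is patients with a baseline value and at least one post-baseline assessment, with no condition that the baseline be normal. For ECGs (SAP 10.4) one denominator serves actual values and another serves changes. Differing from the laboratory rule contradicts nothing.

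**The case for a change.** The best case for the concern is that a reader should not have to add categories from one table, or subtract a row of another, to learn how many patients newly developed serious ideation. The distribution is not split by Baseline level. The subtraction is exact only if nobody entered at level 4 or 5, Baseline is not missing, and both displays use the same patients. If someone was enrolled despite 2a or 2c, the top two categories also pick up (4,4), (4,5), (5,4) and (5,5), giving 8 + 4 = 12 pairs. The text on the listing names lifetime history and post-baseline values but not the Baseline value, so it may not show the shift directly. Read by its label alone, the row can only understate.

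These points are accurate, and a shift table would be a convenient display. But they describe layout. The exceptions need an enrollment deviation, a missing Baseline or mismatched patient sets. Nothing in the documents requires emergence of serious ideation to start from level 0 to 3.

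The denominator point is weaker. It applies equally to the other two emergence rows. A percentage of the whole analysis set is also a legitimate quantity to compare between randomized arms. In addition, SAP Section 2 places the specifications of tables and listings in a separate document, where a row denominator would naturally be found and which is not available here.

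**Conclusion.** The concern does not hold. The row is narrower than its short label suggests, but its definition is explicit and fits the other rows. The patients it leaves out are fully counted, by treatment group, in the DBTP distribution planned in the same section. The effect on results is nil: these summaries are descriptive, no test is attached to them, and no data go uncollected or unreported.

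This rests on exclusions 2a and 2c being followed, so that no one starts treatment at level 4 or 5. In the C-SSRS columns of Protocol Table 9-1 that pool in the 100 patients randomized before Amendment 2.0, it also assumes that the same C-SSRS exclusions applied under the original protocol, which is not among the documents. The columns for patients randomized after that amendment do not need this assumption.

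The counts 2, 6, 8 and 14 are numbers of possible level changes, not of patients. How many patients enter at levels 1 to 3 is not given. Entry at those levels may be further limited by the exclusions for investigator-judged suicide risk and for a score of 4 or more on MADRS item 10. Choosing a different baseline condition for this row is a matter of presentation.
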